6.4 Screening, consent, and experimental procedures

Screening, consent for participants in Kinneret Sr Apartments

Staff from this site will introduce the researchers to older adults in Kinneret Sr Apartments for performing recruitment. Our team will meet with participants at a meeting room in Kinneret Sr Apartments. We will screen participants by asking their age and language (English or Spanish). We will also ask if they have a medical condition precluding balance test and/or physical activity (e.g., shortness of breath, unable to stand on the balance plate) or currently receiving treatment from a rehabilitation facility or have a metal implant. Finally, we will assess their cognition using the Memory Impairment Screen (MIS) test. It will take about 3-5 mins (total) per person.

We will complete the informed consent in a private and quiet place in Kinneret Sr. apartments for participants who meet the inclusion criteria. If the participant needs time to discuss taking part in this research study with family members, friends, and other care providers, we will reschedule a visit for completing surveys and tests.

If he/she indicates that she/he is ready and wants to participate in this research study, she/he will be asked to complete the questionnaires such as socio-demographics and fear of falling.

Procedure for contacting participants for timepoint 2:

Screening, consent for the general population (outside Kinneret)

Our team will meet with each participant (by appointment) in a private and quiet place at the UCF College of Nursing. Participants will complete a simple COVID-19 self-checker questionnaire before coming to the UCF campus. We will screen participants by asking their age and language (English or Spanish). We will also ask if they have a medical condition precluding balance test and/or physical activity (e.g., shortness of breath, unable to stand on the balance plate) or currently receiving treatment from a rehabilitation facility, or having a metal implant. Finally, we will assess their cognition using the Memory Impairment Screen (MIS) test. It will take about 3-5 mins (total) per person.

We will complete the informed consent in the participants who meet the inclusion criteria. If the participant needs time to discuss taking part in this research study with family members, friends, and other care providers, we will reschedule a visit for completing surveys and tests.

If he/she indicates that she/he is ready and wants to participate in this research study, she/he will be asked to complete the questionnaires such as socio-demographics and fear of falling.

Procedure for contacting participants for timepoint 2:

Experimental procedures for both groups

We will assess the static balance performance using the BBS. Participants will take off their shoes and stand as still as possible on the balance plate with hands on their hips and eyes closed for 2-3 minutes. Participants will then complete the

dynamic balance performance test using the sit to stand by full standing up from a chair as many as possible within 30 seconds.

Participants will be stratified by the FRA matrix.¹⁷ We will continually evaluate across four groups (rational/ incongruent/ irrational/ congruent) to maintain equal cell distribution (30 OAs/group)*.

- 1) rational FRA: low FOF [Short Fall Efficacy Scale International (short FES-I) score ≤ 10] and aligned with normal balance (BBS score = 0-30).
- 2) incongruent FRA: low FOF (short FES-1 score ≤ 10) despite poor balance (BBS score= 31-100).
- 3) irrational FRA: high FOF (short FES-I score > 10) whereas normal balance (BBS score= 0-30).
- 4) congruent FRA: high FOF(short FES-I score > 10) and poor balance (BBS score= 31-100).¹⁷

**Please note: This is not an intervention study and subjects will not be assigned to the study group.*

They will perform the hand-grip strength and sit to stand tests. Hand-grip strength will be measured in kilograms (kg) as maximal isometric force achieved on a hand-grip dynamometer. This test will be administered with participants sitting in a chair with feet flat on the floor and the elbow bent at 90°. The dynamometer will be placed in the hand and adjusted so the palm side of the grip will be at the palm, and the front end will be lined up between the joints of the medial and distal phalanges. The grip size will be adjusted so that the second metacarpals were flat with a 90° bend at the knuckles. Participants will be asked to squeeze the strength gauge as hard as possible for 3–5 seconds. Three trials on each hand will be performed with 30-s of rest given between trials. Participants will complete the sit to stand by full standing up from a chair as many as possible within 30 seconds.⁷⁸

Body composition will be tested, and all participants will be asked to empty their bladder, remove socks, shoes, and metal objects (e.g., watches, jewelry) before testing. The participants will be instructed to avoid exercise 6-12 hrs, eating 3-4 hrs, and drinking alcohol/coffee 24 hrs before the body composition test. We will obtain weight from a scale. Participants will be asked to stand for 10-15 mins before testing in a standing position or sit for 10-15 min for a seated position or lie down for 15 mins before testing in a supine position. The RA will present a photo of wipe hands and feet using an InBody tissue (optional).

The RA will also present photos of how to place the touch-type electrodes (labeled LT or RT) at the left and right ankles, middle fingers, and thumbs.

The participants will then place the touch-type electrodes to their left and right ankles, middle fingers, and thumbs. They will hold this position for one minute as the Bioelectrical Impedance Analysis (BIA) device; a minute electrical current will be conducted through the body to determine body composition. The participants will then remove the touch-type electrodes from their left and right ankles, middle fingers, and thumbs. The BIA machine is a widely used commercial device that is FDA approved. There are no risks or discomforts associated with the use of bioelectrical impedance analysis.

Participants will then be instructed to wear the ActiGraph GT9X Link wireless activity monitor on the non-dominant wrist for 7 consecutive days. Participants can remove the monitor only for imaging studies. Each participant will be asked to continue their normal activities while wearing the device. Written instructions will be provided to participants for the use of ActiGraph. The questionnaires and instructions will be provided in English or Spanish by bilingual research assistants (RAs) who will be trained and randomly monitored to ensure quality and consistency in administering questionnaires and tests. Participants will be

provided a phone number for the study team if they have questions about using the activity monitoring device.

Lastly, participants will be asked (using our evaluation form) about their reactions to the questions and technology (i.e., what they thought about the questionnaires and technology) and let them describe any concerns or problems in wearing the device (e.g., uncomfortable to wear during walking). We will provide feedback on the BBS and BIA test results, and participants will receive \$30 Walmart gift card upon completion of the study.

After 7 days of wearing ActiGraph, the participants will return the monitoring device via mail (we will provide pre-paid mailers) or schedule a date/time for picking it up. Participants will leave the device in front of their place.

- Please see Appendix A for a demographic survey
- Please see Appendix B for the Memory Impairment Screen (MIS)
- Please see Appendix C for Patient Health Questionnaire-9 (PHQ-9)
- Please see Appendix D for the Geriatric Anxiety Inventory-Short form (GAI-SF) and Day-to-Day Experiences with the trait Mindful Attention Awareness Scale (MAAS).
- Please see Appendix E for Short Fall Efficacy Scale International (short FES-I) and behavioral changes related to fear of falling
- Please see Appendix F for hand-grip strength test and static balance performance test
- Please see Appendix G for dynamic balance performance test (Sit to stand) and
- Please see Appendix H for Bioelectrical Impedance Analysis (BIA)
- Please see Appendix I for ActiGraph GT9X Link wireless activity monitors and the Rapid Assessment of Physical Activity (RAPA)
- Please see Appendix J for Evaluation form of acceptability of technology and procedures and the short version of Senior Technology Acceptance

6.5 *NA*, No plan for long-term follow-up in this study.

6.6 *NA*

7.0 **Data and Specimen Banking***

NA

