1.0 Study Summary

Study Title	Technology-based fall risk assessments for older adults in low-income settings
Study Design	We will use a cross-sectional design to address our aims and test hypotheses.
Primary Objective	Examine the associations among fall risk appraisal, body composition, and physical activity.
Secondary Objective(s)	-Examine the feasibility of recruitment (e.g., how many older adults (OAs) need to be screened to recruit the sample?), especially during the COVID-19 pandemic, and acceptability of technologies and procedures for use among OAs in low-income settings. -Determine the dynamic relationships between fall risk appraisal, body composition, physical activity, and behavioral changes related to fear of falling
Research Intervention(s)/ Investigational Agent(s)	NA
IND/IDE #	NA
Study Population	Adults aged 60 years and older
Sample Size	120 participants for timepoint 1 60 participants for timepoint 2
Study Duration for individual participants	Total 9 days with two visits (105-158 mins, total)
Study Specific Abbreviations/ Definitions	Older Adults (OAs) Physical Activity (PA) Fall Risk appraisal (FRA) Fear of Falling (FOF) Assistive Health Technology (AHT) BTrackS Balance Plate (BBP) BTrackS Balance System (BBS) Body Mass Index (BMI) Bioelectrical Impedance Analysis (BIA) Fall-Efficacy Scale International (FES-I) Patient Health Questionnaire-9 (PHQ-9)

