(FRA), a condition in which there is a discrepancy between perceived fall risk (levels of FOF) and physiological fall risk (balance performance).^{17, 18} Measuring FRA in OAs can be challenging due to self-report bias and cognitive deficit.^{19, 20} Using both subjective and objective measures provides better fall risk assessment among OAs.^{20, 21} Thus, we developed a *fall risk appraisal matrix*, a graphical grid categorizing levels of FOF and balance performance into four quadrants (Fig 1): **1) rational FRA** (low FOF and normal balance), **2) incongruent FRA** (low FOF despite poor balance), **3) irrational FRA** (high FOF despite normal balance), and **4) congruent FRA** (high FOF and poor balance).¹⁷ In our pilot study (N=102), we measured FOF by a questionnaire and balance performance using a portable and novel force balance plate (BTrackS Balance System; **BBS**). We found that 40% of OAs had maladaptive FRA. Of this group, 19% with incongruent FRA and 30% with irrational FRA reported falling in the past year.¹⁷ OAs with congruent FRA were 3.29 times more likely to fall than those with rational FRA.²² However; our sample included only 11% of low-income OAs.

3.3

Maladaptive FRA may impede low-income OAs participation in PA and can result in social isolation.^{20, 23} Irrational FRA serves as a barrier, creating an irrational fear that inhibits OAs from staying active. Conversely, incongruent FRA can act as an impediment to OAs' safety by fabricating a sense of wellbeing when more caution is warranted. Rational FRA is a crucial component of regular engagement in PA.²⁴ However, research has not examined the association between FRA and PA among low-income OAs. We will examine the association between FRA and PA among low-income OAs.

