10.0 Inclusion and Exclusion Criteria*

10.1

We will screen individuals who will be eligible to participate based on the inclusion and exclusion criteria listed

10.2

Participants will be enrolled if they meet all of the following inclusion criteria: 1) ≥ 60 years of age; 2) no marked cognitive impairment [Memory Impairment Screen (MIS) score ≥5], 3) speak English or Spanish, and 4) live in Kinneret Sr. Apartments.

Exclusion criteria:1) a medical condition precluding balance test (e.g., unable to stand on the balance plate) and/or PA (e.g., shortness of breath; feeling pressure when performing PA); or 2) currently receiving treatment from a rehabilitation facility, or 3) have a metal implant.

10.3

We will exclude all the special populations:

- Adults unable to consent
- Individuals who are not yet adults (infants, children, teenagers)
- Pregnant women
- Prisoners

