13.0 Recruitment Methods

13.1 *Describe when, where, and how*

Approximately 150-200 older adults in Central Florida and Kinneret Sr Apartments will be screened to enroll 120 older adults in this study.

For the Kinneret Sr Apartments, staff from this site will introduce the researchers to older adults for performing recruitment. Our team will meet with participants in a common room or a meeting room in Kinneret Sr Apartments for screening participants.

In the general population, we will recruit them via social media, flyers, and word of mouth.

The research team will follow the UCF COVID-19 Human Subject Research Standard Safety Plan and maintain a log that tracks screening, eligibility, contact, and recruitment.

Approximately 60 adults of the 120 adults who participated at timepoint 1 will be contacted for enrollment for timepoint 2. We will contact participants who elected to be contacted for future studies in their original consent form.

13.2 *Source to subjects*

-Kinneret Sr Apartments, Orlando, FL (Please see Table in Section 24 for the source of subjects).

-General population who are living in Central Florida

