17.0 Data Management* and Confidentiality

17.1

Data Analysis. All analyses will be performed in SPSS version 25 or SAS version 9.4 with sufficient annotation for reproducibility. Descriptive and exploratory analyses will be performed first to investigate distributional assumptions. Although no differences are hypothesized, descriptive subgroup analyses by sex will be conducted.

Aim 1. Examine the feasibility of recruitment, especially during the COVID-19 pandemic and acceptability of technologies and procedures for use among OAs in low-income settings. We will assess the ability to recruit the sample by calculating the proportions of low-income OAs: (a) recruited out of the total screened, and (b) who completed all study procedures. We will track the number of days and time spent to recruit the sample. The results will inform planning for future larger studies. The acceptability of the technologies and procedures will be examined based on an evaluation form (e.g., what they thought about the questionnaires and technology) and their recommendations. We will identify code, categorize participants' responses, and determine the frequency for each category. Demographic data, including essential characteristics of OAs will be obtained for study participants. We anticipate no

more than 3% missing values on any one item, as data will be collected in person on-site.

Aim 2. Examine the associations among fall risk appraisal, body composition, and physical activity.

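### The study targets low-income older adults, but the visible eligibility and screening text has no income item; the only proxy, Kinneret residence, conflicts with an uncapped general-population source.

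*Combined protocol and SAP*

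**What the plan says.** **Target population.** The title in Section 1.0 is "Technology-based fall risk assessments for older adults in low-income settings", and Aim 1 in Section 2.0 refers to the same settings. Section 3.2 reports as a limitation of the pilot (N=102) that "our sample included only 11% of low-income OAs". Section 3.3 then commits the study: "We will examine the association between FRA and PA among low-income OAs". The Aim 1 analysis in Section 17.1 is based on "calculating the proportions of low-income OAs: (a) recruited out of the total screened".

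**Who is admitted.** Section 1.0 gives the study population as "Adults aged 60 years and older". The inclusion criteria in Section 10.2 are age, a Memory Impairment Screen score of at least 5, and then "3) speak English or Spanish, and 4) live in Kinneret Sr. Apartments". The three exclusions concern medical conditions, rehabilitation treatment and metal implants. None mentions income.

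**Screening.** Section 6.4 gives nearly identical scripts for Kinneret and for people outside it: "We will screen participants by asking their age and language (English or Spanish", then medical condition, rehabilitation, metal implant and the memory screen.

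**Second source.** Section 13.1 says "In the general population, we will recruit them via social media, flyers, and word of mouth". Section 13.2 lists the Central Florida general population as a source, and Section 22.1 gives it its own consent location. No cap or quota by source is stated.

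**Socioeconomic data.** Table 1 in Section 6.2 lists socioeconomic status in the self-report questionnaire, which Section 6.4 places after consent. Section 17.1 does not name it as a covariate, a subgroup or a restriction.

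**The concern.** The population named in the question is not the population that the operative rules select. The only rule that could stand in for a low-income setting is Kinneret residence, and the recruitment, screening and consent sections all run a second stream that this rule would bar. The sponsor has to reconcile these sections. If it does so by dropping the residence criterion, the last link between eligibility and a low-income setting goes with it.

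Two results would be affected. The Aim 2 associations could describe a mixed-income sample, although Section 3.3 promises an association among low-income older adults. The Aim 1 recruitment proportion would have low-income enrolees over a denominator of all incomes. It could be calculated, but it would not be the recruitment rate among low-income people that a later study in this population needs for planning.

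**Working it through.** **1. The sections side by side**

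| Item | Where | Income used? |
|---|---|---|
| Title, Aim 1, background | 1.0, 2.0, 3.1-3.3 | Yes, defines the target |
| Inclusion and exclusion criteria | 10.2 | No; Kinneret residence is the only proxy |
| Screening scripts, both sources | 6.4 | No |
| General-population source | 6.4, 13.1-13.3, 22.1 | No; uncapped |
| Socioeconomic questionnaire item | 6.2 (Table 1), 6.4 | Recorded after consent only |
| Aim 1 analysis | 17.1 | Yes, needs low-income status |
| Aim 2 models | 17.1 | No |

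**2. Possible composition of the sample.** The documents give neither the split between sources nor the low-income share of open-source recruits, so this is an illustration. Let g be the number of the 120 from the open source and p the low-income share among them, and assume that every Kinneret resident is low-income. The number outside the target is g × (1 − p). For p, I use the two shares in the plan: 11% (pilot, Section 3.2) and 30% (US older adults below 200% of the poverty line, Section 3.1).

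| g | p = 30% | p = 11% |
|---|---|---|
| 30 | 30 × 0.70 = 21 (18%) | 30 × 0.89 = 26.7 (22%) |
| 60 | 60 × 0.70 = 42 (35%) | 60 × 0.89 = 53.4 (45%) |
| 90 | 90 × 0.70 = 63 (53%) | 90 × 0.89 = 80.1 (67%) |

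Percentages are of 120. If outreach is in fact aimed at low-income people, p is higher and these numbers fall; at p = 100% they are zero.

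**3. What Aim 1 measure (a) would show.** Section 13.1 plans 150-200 screened for 120 enrolled, a yield of 120/200 = 60% to 120/150 = 80%. Assume that this yield is the same at every income. With g = 60 and p = 30%, 120 − 42 = 78 enrolees are low-income. The measure as worded is then 78/200 = 39% to 78/150 = 52%, although 60-80% of the low-income people screened were enrolled. The gap reflects only the income mix of those screened. The logged screening data cannot remove it, because income is not recorded for people who are screened but not enrolled.

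**4. What a low-income analysis set costs in precision.** With g = 60, the low-income set is 78 (p = 30%) or 120 − 53.4 = 66.6 (p = 11%). If they spread evenly over the four appraisal groups, each holds about 78/4 = 19.5 or 66.6/4 = 16.7 people instead of the planned 30. Standard errors for group comparisons grow by √(120/78) = 1.24 or √(120/66.6) = 1.34.

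On the plan's own power inputs (Section 17.1: SDs 7.91 and 7.78, pooled 7.845; balance-score difference 5; two-sided 0.05), power for two groups of n is Φ(5 / (7.845 × √(2/n)) − 1.96):

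- n = 60: 94%
- n = 39: 80%
- n = 33.3: 74%

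These inputs need only 39 per group, or 78 in total, for 80% power, so they do not reproduce the stated 120. That is a separate matter.

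**5. What a hard income criterion would cost.** With yield y on the other criteria, 60 Kinneret enrolees and 60 low-income enrolees from the open source, the number screened is 60/y + 60/(y × p):

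- p = 30%: 75 + 250 = 325 (y = 0.8) to 100 + 333 = 433 (y = 0.6)
- p = 11%: 75 + 682 = 757 to 100 + 909 = 1,009

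The plan is for 150-200.

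**The case against.** Much of the case on the other side is sound, and it limits the point in five ways.

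- **Eligibility.** A reader might infer that the rules admit anyone in Central Florida aged 60 or over. They do not: Section 10.2, read literally, admits nobody outside Kinneret, and the screening exclusions apply as well. The income gap takes effect only if the conflict is resolved in favour of the open source.
- **Aim 1(a).** A reader might infer that it cannot be formed. As worded, the denominator is everyone screened, which the log supplies. The numerator could come from the socioeconomic item if that item permits classification. The measure is computable but answers a different question.
- **Pilot limitation.** A reader might infer that the study would simply repeat it. The scenarios above leave about 33-82% of the sample low-income, against 11% in the pilot. Section 3 also gives other reasons for the study, including objective measurement.
- **Aim 2.** The primary objective and hypotheses H2.1-H2.3 name no income limit. Because socioeconomic status is collected, a low-income analysis may be recoverable after enrolment, so the aim is not lost.
- **Unseen text.** Section 13.2 points to a table in Section 24, and Section 13.4 to the printed advertisement. Neither was available, and either may describe the income profile of the sites or targeted outreach. The revision log also shows an intention to recruit low-income older adults in Central Florida.

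What stands is narrower. Targeted outreach would raise the low-income share, but no visible criterion, screening question or analysis rule ensures or verifies it.

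**Conclusion.** The point holds as a should-fix. The visible criteria and screening script contain no income item, the one proxy contradicts the open source, and no named analysis uses the socioeconomic data. If the open source stays, Aim 2 could describe a mixed-income sample, and Aim 1(a) would not be a recruitment rate among low-income people.

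The size is illustrative: 42-53 of 120 (35-45%) outside the target, with half the sample from the open source, all Kinneret residents low-income, and an open-source low-income share of 11-30%. Other splits give 18-67%. The documents fix none of these inputs, so the range shows what the rules permit and is not a forecast.

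**What to change.** Reconcile Section 10.2 with Sections 6.4, 13 and 22.1, and at the same time:

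1. Add one question on income, or on residence in income-restricted housing, to the screening script and log for both sources. State the study's definition of low-income; the 200% poverty line in Section 3.1 is a background statistic and has not been adopted as a definition. Report Aim 1(a) also with low-income people screened as the denominator.
2. Prespecify that conclusions about low-income older adults in Aims 1 and 2 rest on the low-income participants, with the full sample reported alongside. For people already enrolled, use the socioeconomic item in the demographic survey if it permits classification; Appendix A was not available to check.
3. If this is not done, state that the Aim 2 conclusions apply to a mixed-income sample.

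The cost is one extra question, a short amendment, and a smaller analysis set: in the illustration, 67-78 people, with standard errors 24-34% larger. Income cannot be recovered from the log for people already screened but not enrolled. Making income a hard inclusion criterion for the open source is optional. It would keep the full 120 in the target population, but could raise screening from 150-200 to about 325-433 at a 30% share, and further at a lower one.

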3.0 Background*

3.1

[figure not shown]
More than 15 million (30%) OAs in the US have incomes below the 200% of poverty line.^{1, 2} Poverty rate increases with age, and is higher among women, Blacks and Hispanics, and individuals with poor health.¹ OAs who live in low-income communities are less likely to engage in PA,³⁻⁵ defined as any bodily movement produced by skeletal muscle that results in energy expenditure.⁶ Lack of PA is related to chronic conditions and reduced quality of life among low-income OAs.^{7, 8} Limited data suggest that OAs who overestimate their fall risk and report fear of falling (**FOF**) are less likely to participate in PA, and the association between FOF and PA intensity differs by fear severity.⁹ Changes in body composition also have a significant impact on functional capacity and quality of life.¹⁰ However; these studies have not included OAs from low-income settings, who are more likely to report falls in the prior year.¹¹ Recent systematic reviews found that most studies have not used objective measures of fall risk and PA.^{5, 12} We will use objective measures of body composition, balance performance, and PA among OAs from low-income settings.

Additionally, up to 50% of OAs who have FOF limit their daily physical activity (**PA**) because of the fear.¹³ The COVID-19 pandemic is causing increased fear and related to perceived risks for loved ones and health anxiety.¹⁴ Physical distancing and fear of the virus have led to reductions in OAs' use of routine healthcare and performing daily PA.¹⁵ With the high levels fear; individuals may not think rationally when reacting to COVID-19 and taking care of themselves.¹⁶

3.2

One-third of OAs have maladaptive **fall risk appraisal**

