6.2 Provide a description of all research procedures

We will administer the study instruments which consist of objective and subjective measures (see Table 1) for total 120 participants. Participants will complete questionnaires about OA's characteristics, socio-demographic, medical history, cognition, depressive symptoms, anxiety,

and FOF. We will also assess static balance performance using the BTrackS Balance System^{43, 44}, assess dynamic balance using a sit to stand test, assess body composition using the Bioelectrical Impedance Analysis device⁴², and assess handgrip strength test using a hand-grip dynamometer (JAMAR 5030J1). They will wear an accelerometer-based physical activity device for 7 consecutive days.

Table 1. Description of study variables and instruments

Variable	Instrument	Description
OA's Characteristics - Socio-demographics and medical history -Cognition - Depressive symptoms -Anxiety and day-to-day experiences	Self-report questionnaire - Memory Impairment Screen (MIS) ⁵¹⁻⁵³ -Patient Health Questionnaire-9 (PHQ-9) ^{54, 55} -Geriatric Anxiety Inventory-Short form (GAI-SF). ⁵⁶⁻⁵⁸	e.g., age, gender, living status, education level, socioeconomic status, perceived general health, comorbidities, FOF, frailty, fall risk, and social network. - The Memory Impairment Screen (MIS) is a widely used test of cognitive function and screening Alzheimer's disease among OAs. It is a 4-minute, four-item delayed free and cued recall memory test with controlled learning and high discriminative validity. The maximum score for the MIS is 8 and if score 5-8=no cognitive impairment and score ≤ 4 =possible cognitive impairment. -10 items (e.g., feeling tired) on a 4-point scale; measures symptoms of depression within the prior 2 weeks; Total scores range 0-27, scores ≥ 10 moderate depression. ⁵⁴ Cronbach's alpha=0.89 among OAs. ^{54, 55} - The GAI-SF is an abbreviated version of GAI comprising only five of the original items. The GAI-SF has good internal consistency, convergent and divergent validity, and was highly

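### Keeping 30 people in each of four fall-risk-appraisal cells within 120 enrolled needs 50% maladaptive appraisal; the plan's own rates (one-third, 40%) do not support that

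*Combined protocol and SAP*

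**What the plan says.** - **Cell sizes.** Section 6.4 classifies participants by short FES-I score (10 or below, or above 10) and BTrackS (BBS) percentile (0–30, or 31–100). It says the four groups will be evaluated continually "to maintain equal cell distribution (30 OAs/group"). A footnote adds that this is not an intervention study and that nobody is assigned to a group.
- **Total.** Section 6.2 plans the "objective and subjective measures (see Table 1) for total 120 participants". Section 13.1 says "Approximately 150-200 older adults in Central Florida and Kinneret Sr Apartments will be screened to enroll 120 older adults in this study". Section 13.5 expects all 120 to complete.
- **Order of events.** Screening in Section 6.4 covers age, language, medical exclusions and the memory screen. Then: "We will complete the informed consent in the participants who meet the inclusion criteria". Only after agreeing to take part is a person in the position that "she/he will be asked to complete the questionnaires such as socio-demographics and fear of falling", and the balance test follows.
- **Expected frequency.** Section 3.2 defines maladaptive FRA as a discrepancy between perceived and physiological risk, which is the incongruent and irrational cells. It opens with "One-third of OAs have maladaptive" FRA, and reports from the pilot (N=102): "We found that 40% of OAs had maladaptive FRA". It also warns that "our sample included only 11% of low-income OAs".
- **Use of the cells.** Section 17.1 makes rational FRA the base group and compares each of the other three cells with it.

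**The concern.** Four cells of 30 use up all 120 places, so equal cells require exactly half the sample to be maladaptive. Both rates the plan cites are below one half. A person's cell is not known until after consent and two study measurements, so the extra 30 to 80 people screened are never classified by cell and cannot balance the cells as the procedures are written. The supplied text gives no rule for closing a full cell, for enrolling beyond 120, or for someone tested after their cell is full.

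Aim 2 is the primary objective, and the precision of its three contrasts depends on cell sizes. Thirty per cell is the only cell size the plan states. There is also a practical risk: staff trying to hold cells at 30 without a written rule might turn away consented people, which would disturb the recruited and completed proportions reported under Aim 1.

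**Working it through.** **Inputs.** Four cells of 30 (Section 6.4); 120 enrolled (Sections 1.0, 6.2, 12.1, 13.1); maladaptive rate 1/3 or 0.40 (Section 3.2); pilot N=102 (Section 3.2). Assumed: the pilot's 40% was 41 of 102.

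**1. The plan's own figure.** 4 × 30 = 120, so the target matches the total exactly. The two maladaptive cells need 2 × 30 = 60, and 60/120 = 50%.

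**2. Expected counts if the 120 are enrolled without regard to cell.**

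| Maladaptive rate | Maladaptive, 120 × rate | Average per maladaptive cell | Rational + congruent | Short of 60 by |
|---|---|---|---|---|
| 1/3 | 40 | 20 | 80 | 20 |
| 0.40 | 48 | 24 | 72 | 12 |

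**3. Chance of at least 60, same condition.** With X ~ Binomial(120, p):

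| p | P(X ≥ 60) | Central 95% range of X |
|---|---|---|
| 1/3 | 0.0001 | 30–50 |
| 0.40 | 0.017 | 38–59 |
| 0.45 | 0.16 | – |
| 0.50 | 0.54 | – |

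The pilot rate is itself uncertain. Taking 41/102 with a Jeffreys prior, p ~ Beta(41.5, 61.5), the predictive probability of at least 60 is about 0.08. The 95% Wilson interval for 41/102 is about 31% to 50%.

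Reaching 60 in total is necessary but not sufficient, because each maladaptive cell must reach 30. Under an assumed even split of the maladaptive group, the simulated chance of both doing so is below 0.0001 at one-third and about 0.004 at 40%.

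**4. If quota sampling is meant.** The average number to be classified on both short FES-I and BBS to find 60 maladaptive people is 60/p: 60/0.40 = 150, or 60/(1/3) = 180. The need is greater if the two maladaptive cells are not equally common. The instruments are planned for 120.

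**5. Effect on an Aim 2 contrast.** The standard error of a difference in means is proportional to √(1/a + 1/b) for cells of size a and b. Detectable differences are for a two-sample t-test, two-sided 0.05, 80% power. The 24/36 and 20/40 rows assume an even split within each pair of cells.

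| Maladaptive vs rational | SE relative to 30 vs 30 | Detectable difference (SD) |
|---|---|---|
| 30 vs 30 | 1.00 | 0.74 |
| 24 vs 36 (40%, even) | 1.02 | 0.75 |
| 20 vs 40 (1/3, even) | 1.06 | 0.78 |

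The documents do not give the splits, and uneven ones move the result either way. For illustration, 12 vs 36 gives √(1/12 + 1/36)/√(2/30) = 1.29, and 30 vs 60 gives √(1/30 + 1/60)/√(2/30) = 0.87.

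**The case against.** **It is a quota.** Continual evaluation to keep cells equal is quota language, and the footnote on assignment rules out allocation to groups, not the closing of a full cell. On that reading the binomial probabilities do not apply, and this stands: they describe unselected enrolment only. But the quota reading moves the difficulty rather than removing it. An average of 150 to 180 people would need the short FES-I and BBS, against 120 planned. The 150–200 screened overlap that range numerically, but screening does not measure FRA, and the same people must also absorb ineligibility and refusals.

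**The rates may not carry over.** This also stands. The pilot was only 11% low-income, its questionnaire and cut-off are not named in Section 3.2, and 50% sits at the upper edge of the interval around its rate. A reader might infer that equal cells cannot be achieved; the documents do not show that. They show only that no figure in the plan supports 50%. The 19% and 30% quoted for the incongruent and irrational groups do not fill the gap: they read as the share in each group who had fallen, not as cell shares.

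**Little depends on it.** Largely right. Regression and ANOVA accept unequal groups. A reader might infer that the study's power claim fails, but the sample-size statement in Section 17.1 compares BBS scores between two physical-activity groups and never uses 30 per FRA cell. Nor can one firm range for the loss of precision be attributed to the plan, since the splits are unknown.

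**Conclusion.** The point holds as a mismatch between a stated group size and the plan's own figures. At N=120 the plan would maintain 60 maladaptive participants, while its cited rates predict 40 to 48 under unselected enrolment. Under quotas, it would need to classify more people than it plans to test. Thirty per cell is unsupported, not impossible.

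The consequence is confined to the precision of the Aim 2 contrasts with rational FRA. Under an assumed even split the loss is small (0.75–0.78 SD detectable, against 0.74 SD); uneven splits could make it larger or turn it into a gain. The Aim 2 analysis remains valid. The conclusion rests on the one-third and 40% rates applying roughly to this population, and the 0.08 figure also on the assumed pilot count. The correction is worth making because it is cheap and concerns the primary objective.

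**What to change.** In Section 6.4:

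1. Restate 30 per group as a target, not a size that will be maintained.
2. State the distribution expected at N=120 and the cited rates: about 40–48 maladaptive participants in total (averaging 20–24 per maladaptive cell) and 72–80 in the rational and congruent cells combined. Say that the splits within each pair are unknown and that the rates come from a largely different population.
3. State that all 120 enrolled complete all procedures and are analysed whatever their cell. This leaves the Aim 1 proportions undisturbed.

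In Section 17.1, commit to reporting the achieved cell sizes and a 95% confidence interval for each contrast with rational FRA.

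**Cost.** No extra participants, visits or tests. The stated group size becomes less favourable than 30 per cell, and the plan gives up the appearance of guaranteed balance.
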